4.3. Summary of Relevant Clinical Studies

Previous studies in adults with DPT thermal burns have demonstrated that StrataGraft skin tissue is generally safe with salutary clinical outcomes in regard to closure of DPT burns and elimination of autograft placement in the majority of subjects.

The Phase 1b study, "Open-label, Controlled, Randomized, Multicenter, Dose Escalation Study Evaluating the Safety and Efficacy of StrataGraft® Skin Tissue in Promoting the Healing of the Deep Partial-Thickness Component of Complex Skin Defects as an Alternative to Autografting," (STRATA2011) was an open-label, dose-escalation, multicenter study evaluating the safety, tolerability, and efficacy of StrataGraft skin tissue in promoting the healing of complex skin defects containing intact dermal elements. In this study, StrataGraft skin tissue was applied once to DPT burns to assess autologous tissue regeneration with reduction or elimination of

Protocol MNK01053115

StrataGraft

Amendment 1

autografts. This study included subjects with thermal burns of 3 to 49% TBSA. Each subject had 2 comparable burn wound areas identified, excised to remove nonviable tissue, and randomized to receive StrataGraft skin tissue or autograft. Thirty subjects were enrolled with 10 subjects in Cohort 1 receiving up to 220 cm² of refrigerated StrataGraft skin tissue and 10 subjects in Cohort 2 receiving up to 440 cm² of refrigerated StrataGraft skin tissue. Ten subjects in Cohort 3 received up to 440 cm² of thawed cryopreserved StrataGraft skin tissue. None of the subjects treated with StrataGraft skin tissue exhibited any significant safety concerns and none underwent autografting prior to Day 28. Additionally, 27 of the 28 per-protocol subjects (96%) exhibited complete wound closure of StrataGraft treatment sites at Month 3. Molecular analysis of biopsies taken from treated wound sites at Month 3 demonstrated no evidence of StrataGraft skin tissue DNA, indicating that the cellular components of StrataGraft skin tissue were no longer present.

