6.3. Treatment Assignment

Subjects who meet all inclusion criteria will receive StrataGraft skin tissue treatment. Subjects are considered enrolled into the study once they have StrataGraft skin tissue treatment applied to a burn site. Subjects will receive 1 application of StrataGraft skin tissue(s) to no more than 3 burn sites with no more than 20 StrataGraft skin tissues applied to the burn sites and a total study treatment area of no more than approximately 2000 cm².

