3.7 Treatment and Exposure

The number of subjects with 1, 2, and 3 burn sites, and numbers of StrataGraft constructs applied (per site and total per subject) will be summarized.

The observation duration from Day 1 (application of StrataGraft) to end of study will be summarized.

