3.8 Efficacy and Safety Analysis

There is no hypothesis testing for the study. All analyses are descriptive.

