3.8.2 Other Endpoint Analyses

The other endpoints of this study are:

- **Proportion of subjects with confirmed complete wound closure of all treatment sites without autograft (i.e., complete re-epithelialization without drainage and subsequently verified with confirmation assessment) on or before Week 12, supported by photodocumentation.**

Complete wound closure is defined as 100% skin re-epithelialization in absence of drainage and without autograft placement. Successful wound closure in this study requires that complete wound closure on or before Week 12 is achieved without autograft placement and is confirmed at least 14 days following the initial observation of complete closure.

The investigator will evaluate the confirmation of complete wound closure either by direct clinician observation or by subject-provided photodocumentation.

The proportion of subject with all confirmed complete treatment site closure(s) including two-sided 95% confidence intervals based on the normal approximation to the binomial will be calculated and presented.

- **Proportion of subjects with confirmed complete wound closure of all treatment sites without autograft (verified with confirmation assessment) at each visit, supported by photodocumentation.**

The planned visits are Week 1, Week 2, Week 4, Week 8, Week 12, and Week 24. However, the subjects may show up at any visit, and number and percentage will be summarized. For each visit, the denominator of the proportion of subjects is based on the total number of subjects who provided data for the visit.

- **Proportion of subjects maintaining durable wound closure by Week 24.**

Durable wound closure by Week 24 is achieved when a subject with confirmed wound closure is observed as remaining closed at least 90 days after complete wound closure through Week 24. Two summaries will be performed: 1. Denominator is mITT population 2. The denominator will be based on subjects with confirmed wound closure of all treatment sites without autograft by Week 12. The number, percentage and two-sided 95% confidence intervals based on the normal approximation to the binomial will be calculated and presented.

- **Proportion of treatment sites with confirmed complete wound closure without autograft (i.e., complete re-epithelialization without drainage and subsequently verified with confirmation assessment) on or before Week 12 and supported by photodocumentation.**

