The treatment sites will be analyzed regardless of subject. Treatment site with confirmed wound closure requires treatment site complete closure on or before Week 12 is achieved without autograft placement and is confirmed at least 14 days following the initial observation of complete closure.

The investigator will evaluate the confirmation of complete treatment site closure either by direct clinician observation or by subject-provided photodocumentation.

The proportion of confirmed complete treatment site closure including two-sided 95% confidence intervals based on the normal approximation to the binomial will be calculated and presented.

- **Proportion of treatment sites maintaining durable wound closure by Week 24.**

The treatment sites will be analyzed regardless of subject.

Durable wound closure by Week 24 is achieved when a confirmed wound is observed as remaining closed at least 90 days after a confirmed complete wound closure through Week 24. Two summaries will be performed: 1. Denominator is all treatment sites 2. The denominator will be based on a confirmed treatment site wound closure by Week 12. The number, percentage and two-sided 95% confidence intervals based on the normal approximation to the binomial will be calculated and presented.

- **Time to first confirmed complete wound closure of all treatment sites in a subject without autograft (verified with confirmation assessment at least 14 days later).**

The event for Kaplan-Meier method will be the first occurrence of all confirmed complete wound closure without autograft in a subject (first observation of complete closure verified with a second observation of complete closure at least 14 days later). The time to first confirmed wound closure will be analyzed by the Kaplan-Meier estimation method. The period for this analysis is calculated as (the date of having the first confirmed event – the date of Day 1 + 1). Subjects not having any confirmed complete closure event during the study will have their time censored at the last available date in the study. Kaplan-Meier estimates by StrataGraft treatment area with confirmed wound closure will be presented for the following categories: $\leq 500 \text{ cm}^2$, $> 500 \text{ cm}^2$.

The Kaplan-Meier estimate will be computed to determine the median time to confirmed complete wound closure without autograft placement.

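### The confidence intervals for the pooled site-level closure proportions treat up to three sites from one subject as independent, and are too narrow if those sites are positively correlated

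*SAP*

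**What the plan says.** Protocol 6.3 allows several treated sites per subject: "Subjects will receive 1 application of StrataGraft skin tissue(s) to no more than 3 burn sites". The SAP expects this to occur, since section 3.7 tabulates "The number of subjects with 1, 2, and 3 burn sites".

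SAP 3.8.2 then defines two endpoints whose unit is the site, and says of both: "The treatment sites will be analyzed regardless of subject".

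- **Week 12 confirmed closure.** The planned summary is "The proportion of confirmed complete treatment site closure including two-sided 95% confidence intervals based on the normal approximation to the binomial".
- **Week 24 durable closure.** The same type of interval is planned with two denominators. For the first, "Denominator is all treatment sites"; the second is the sites with confirmed closure by Week 12.

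Three site-level intervals are therefore affected. Neither document mentions a cluster-robust variance, a design effect, GEE or a subject-level bootstrap. The general convention in SAP 3.1 is worded for subjects and also uses the plain normal approximation.

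The corresponding subject-level endpoints in SAP 3.8.2, which require closure of all of a subject's sites, have one observation per subject.

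**The concern.** The binomial variance p(1−p)/S counts each of the S sites as a separate, independent piece of information. Sites on one person share host factors, aftercare and usually the assessor, so their outcomes plausibly go together. If they do, S sites carry less information than S independent observations, and the planned interval claims more precision than the data hold.

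The study tests no hypothesis, so the interval is the only statement of uncertainty a reader gets for these endpoints. SAP section 1 foresees use of the analyses in the study report and possibly in regulatory submissions and manuscripts. Pooling also makes the denominator larger than in the subject-level analysis, so the site-level result can look more precise for a reason the data may not support.

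**Working it through.** The documents state no target precision or interval width, so there is no planned figure to reproduce.

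**Inputs from the documents:** about 100 subjects (Protocol 6.2); at most 3 sites each (Protocol 6.3); two-sided 95% normal-approximation intervals (SAP 3.8.2).

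**Assumptions:** the share of subjects with 1/2/3 sites (three mixes), the ICC, and a closure rate p of 85%. A rate of 96% is added because Protocol 4.3 reports for the Phase 1b study that "27 of the 28 per-protocol subjects (96%) exhibited complete wound closure". That is a per-subject rate at Month 3, so it is only a loose guide.

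**Step 1: planned interval.** Half-width = 1.96 × √(p(1−p)/S). For 60/30/10, S = 150 and the half-width is 1.96 × √(0.85 × 0.15/150) = 5.7 points.

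**Step 2: design effect.** With m sites per subject, DEFF = 1 + (E[m²]/E[m] − 1) × ICC.

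- 80/15/5: E[m] = 1.25, E[m²] = 1.85, DEFF = 1 + 0.48 × ICC
- 60/30/10: E[m] = 1.50, E[m²] = 2.70, DEFF = 1 + 0.80 × ICC
- 30/40/30: E[m] = 2.00, E[m²] = 4.60, DEFF = 1 + 1.30 × ICC

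The true standard error is √DEFF times the planned one:

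| ICC | 80/15/5 | 60/30/10 | 30/40/30 |
|---|---|---|---|
| 0.1 | √1.05 = 1.02 | √1.08 = 1.04 | √1.13 = 1.06 |
| 0.3 | √1.14 = 1.07 | √1.24 = 1.11 | √1.39 = 1.18 |
| 0.7 | √1.34 = 1.16 | √1.56 = 1.25 | √1.91 = 1.38 |

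The limits are DEFF = 1 (every subject has one site, or ICC = 0) and DEFF = 3 (three sites for all and ICC = 1, standard error 1.73 times the planned one).

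**Step 3: coverage of the planned interval.** Beta-binomial simulation, 100 subjects, random site mix, 40,000 runs per cell, p = 85%:

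| ICC | 80/15/5 | 60/30/10 | 30/40/30 |
|---|---|---|---|
| 0 | 94.0% | 94.0% | 94.3% |
| 0.1 | 93.4% | 93.2% | 92.9% |
| 0.3 | 92.0% | 91.4% | 89.4% |
| 0.7 | 89.4% | 87.2% | 83.3% |

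The ICC 0 row shows the loss from the normal approximation alone, 0.7–1.0 point. Subtracting each lower row from it gives the loss from clustering: 0.6–1.4 points at ICC 0.1, 2.0–4.9 at ICC 0.3 and 4.6–11.0 at ICC 0.7.

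The large-sample formula 2Φ(1.96/√DEFF) − 1 agrees in pattern. For 60/30/10 at ICC 0.3 it gives 92.2%.

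**Step 4: high closure rate.** At p = 96%, same mix order, coverage is 88.4/92.9/91.7% at ICC 0 and 83.8/85.8/80.2% at ICC 0.7. Clustering therefore costs 4.6/7.1/11.5 points. The rest, 6.6/2.1/3.3 points, is due to the normal approximation near 100%.

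**Step 5: candidate replacements.** Coverage over all three mixes and ICC 0 to 0.7:

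| Interval | p = 85% | p = 96% |
|---|---|---|
| Cluster-robust, normal approximation | 93.0–94.3% | 85.9–92.8% |
| Wilson, effective size S/DEFF | 94.5–95.6% | 92.0–96.0% |
| Cluster-robust on the logit scale | 94.8–95.5% | 93.2–96.5% |

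A cluster-robust variance alone does not restore coverage at high closure rates.

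**The case against.** The strongest case is that little depends on these intervals. They belong to non-primary endpoints in a single-arm study where "All analyses are descriptive". There is no precision target, and the point estimates do not change. Subject-level intervals for both outcomes are reported alongside, and the 1/2/3-site mix will be tabulated, so a careful reader can see how much clustering is possible. All of this is true. It limits the consequence but does not make the site-level intervals valid as 95% intervals.

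The size is also assumed. At ICC 0.1 the loss is at most 1.4 points of coverage, and the large figures need a high ICC or many multi-site subjects, for which the documents give no evidence. This stands too: only the direction is firm.

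Three further limits apply:

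- The tenths of a point should not be over-read. With the site mix fixed at the stated shares instead of random, coverage at p = 85% and ICC 0 is 92.9/93.7/94.3%. At p = 96%, 30/40/30 and ICC 0.7 it is 77.8% instead of 80.2%. The pattern is unchanged.
- The figures apply directly to the all-site denominators. The second durable-closure denominator has cluster sizes that depend on the data; the same fault applies there, but it was not sized.
- The subject-level intervals are free of the clustering problem only. They use the same normal approximation, whose exact coverage with 100 subjects is 93.3% at 85% and 90.6% at 96%.

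**Conclusion.** The concern holds. As written, the three site-level intervals rest on independence between sites of one subject, and nothing in either document supports that or corrects for it. They are too narrow whenever some subjects have more than one site and the within-subject correlation is positive.

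Under the assumed mixes and ICCs of 0.1 to 0.7, the standard error is understated by a factor of 1.02 to 1.38. Clustering alone takes roughly 1 to 11 points off coverage at 85% closure. The effect is close to nil if few subjects have several sites.

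The primary TEAE endpoint and the pooled point estimates are unaffected, and clustering does not affect the subject-level proportions. This should be corrected, but it does not threaten the study's main conclusion.

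**What to change.** Keep the pooled site proportions as estimates. In SAP 3.8.2, replace the interval method for the three site-level proportions with one that treats the subject as the cluster and behaves well near 100%. Either of these would serve:

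- **Wilson interval with effective sample size S/DEFF.** DEFF is the cluster-robust variance divided by the binomial variance, floored at 1. If every site closes, use the number of subjects as the sample size.
- **Logit-scale interval with a cluster-robust standard error.** This is undefined if every site closes, so a fallback must be named.

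The cost is one SAP sentence and standard code, with no new data. The intervals become somewhat wider. At 85% closure, the mean full width with the Wilson option goes from about 11.3 points to 11.9 (ICC 0.1) or 14.1 (ICC 0.7) for the 60/30/10 mix. For 30/40/30 it goes from about 9.8 points to 10.5 or 13.5. If the sites prove nearly uncorrelated, or few subjects have more than one, the intervals barely change.

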10. ASSESSMENT OF OTHER PRE-SPECIFIED ENDPOINTS

Wound closure

Complete wound closure is defined as 100% skin re-epithelialization in the absence of drainage. Successful wound closure in this study requires that complete wound closure is achieved without autograft placement and is confirmed at least 2 weeks following the initial observation of complete closure. The clinical investigator will evaluate treatment site(s), assess the proportion of the treated wound closed, complete wound closure, and confirmation of complete wound closure either by direct clinician observation or by subject-provided photo-documentation per Schedule of Assessments (Section 6.1.1).

Photo-documentation

Photographs will be taken by the clinician to supplement clinical assessment of percentage epithelialization, complete wound closure, confirmed wound closure, durable wound closure and the POSAS assessments (eg, appearance and cosmesis) of the treatment sites. Photographs taken and submitted by the subject (or other person designated by the subject) may be used for evidence of wound characteristics if a visit is missed or for an unscheduled visit.

Photo-documentation is submitted by the subject beginning at discharge then weekly until Week 12 and then every other week until Week 24. These subject-submitted photos are only possible if the Principal Investigator gives approval for the subject to take off their dressings at home. In the event the dressings are not allowed to be changed at home, no subject photos will be expected or required. Photos submitted during weeks when there are no in-person visits would serve as an allowable proxy for observing wound characteristics. If a subject's wound is noted to be closed for the first time via a submitted photo, that photo should trigger the scheduling of a visit 2 weeks later for confirmation of wound healing. See Manual of Procedures for specific instructions regarding the methodology for obtaining photographs.

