Assessment of wound closure/continued closure			✓	✓	✓	✓	✓	✓	✓
Skin quality outcome of treatment sites							✓	✓	
HCRU Assessments	✓	✓	✓	✓	✓	✓	✓	✓	✓
Biopsies ⁱ							✓		

^aIn public state of emergency situations, the Weeks 1 and 2 visit windows can be expanded to include ± 5 days.

^bIn public state of emergency situations, the Week 4 visit window can be expanded to include ± 12 days.

^bIn public state of emergency situations, the Weeks 8, 12, and 24 visit windows can be expanded to include ± 14 days.

^cThis visit may be scheduled at any time during the study to occur at least 2 weeks after initial observation of complete wound closure.

^dConsent for post study registry can be obtained at any study visit beginning at Screening (together with the consent for the study treatment), during the study treatment, or at the final study visit.

^eAny testing abstracted from the medical record from the time of admission throughout the study treatment period.

^fMay be performed within 48 hours of surgery.

^gAEs will be assessed on an ongoing basis; AEs (serious and non-serious) occurring from time of signing informed consent until completion of the Final Visit and follow-up until resolution of any ongoing TEAE at the time of study treatment completion or subject withdrawal.

^hA weekly photo taken by subject (or designate) of the treatment site(s) for the first 12 weeks and then every other week to Week 24. Photos submitted during a week when there's no in-person visit would serve as an allowable proxy for observing wound characteristics. If a subject's wound is noted to be closed for the first time via a submitted photo that should prompt a confirmation of wound healing visit 2 weeks later.

ⁱBiopsies of a closed wound and of the normal skin will be taken from a subgroup of 10 subjects.

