3 STATISTICAL METHODS AND CONVENTIONS

3.1 General Conventions

- Unless otherwise noted, the number of subjects (N), mean, standard deviation, median, minimum, and maximum will be presented for continuous variables and frequency and percentage of subjects in each category will be presented for discrete variables.
- Unless otherwise noted, confidence intervals (CIs) will be 2-sided 95% CIs.
- Listings will be sorted by subject identification, and date of the procedure or event.
- Statistical analyses will be done using Statistical Analysis Software (SAS[®]) version 9.4 or higher.
- The Kaplan-Meier estimate will be computed to determine the median time to first confirmed complete wound closure without autograft placement (date of closure is the date of the first observation of complete epithelialization without use of an autograft and confirmed with a second observation of complete closure at least 2 weeks after the first.). The 95% CI will be constructed with a generalized Brookmeyer and Crowley method.
- The Proportion and 95% CI of subjects will be calculated using the normal approximation to the binomial distribution.
- Listing will be provided for all related summary tables.

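### The Kaplan-Meier median dates closure at first observation, so as an estimate of when wounds close it is late by an amount that depends on unstated photo uptake

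*SAP*

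**What the plan says.** SAP 3.8.2 gives the method: "The time to first confirmed wound closure will be analyzed by the Kaplan-Meier estimation method". The time variable is defined by "The period for this analysis is calculated as (the date of having the first confirmed event – the date of Day 1 + 1", and the censoring rule is "Subjects not having any confirmed complete closure event during the study will have their time censored at the last available date in the study". SAP 3.1 fixes the event date: "date of closure is the date of the first observation of complete epithelialization without use of an autograft", confirmed by a second observation at least two weeks later. For the median, SAP 3.1 adds: "The 95% CI will be constructed with a generalized Brookmeyer and Crowley method". Protocol 13.3.2 also specifies Kaplan-Meier, with separate estimates for treated areas up to and above 500 cm².

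On when closure can be seen, SAP 3.8.2 states: "The planned visits are Week 1, Week 2, Week 4, Week 8, Week 12, and Week 24". Between visits the schedule of assessments provides for a "weekly photo taken by subject (or designate) of the treatment site(s) for the first 12 weeks and then every other week to Week 24", and Protocol 10 accepts these photos as a proxy in weeks without a visit. They depend on the investigator approving dressing removal at home: "In the event the dressings are not allowed to be changed at home, no subject photos will be expected or required".

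For this endpoint neither document mentions interval censoring, a last date seen not closed, a sensitivity analysis or a split by visit versus photo. SAP 3.8.2 does split in-person from remote assessment for the scar scale.

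**The concern.** A wound closes at some time between the last assessment at which it was open and the first at which it was closed. The analysis uses only the right-hand end of that interval. The interval is about a week for a subject who sends photos and up to four weeks for a subject seen only at Weeks 4, 8 and 12. The same healing can therefore produce different medians according to how often subjects were observed.

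The study tests no hypotheses, so the estimates are its output. The synopsis names this median, and SAP 1 allows the results to go into regulatory submissions or manuscripts. A reader is likely to take it as how long wounds take to heal. The comparison by treated area is open to the same problem if photo use differs between the two groups.

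**Working it through.** **There is no planned figure to reproduce.** The documents give no expected median, healing distribution or photo uptake. All sizes below rest on stated assumptions.

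**Inputs from the documents.** About 100 subjects. Visits at Weeks 1, 2, 4, 8, 12 and 24, so gaps of 1, 1, 2, 4, 4 and 12 weeks. With the +1 convention, Week w falls on day 7w + 1: days 8, 15, 29, 57, 85 and 169. Photos are weekly to Week 12, then every second week.

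**Assumptions.** True closure time is lognormal with SD of log time 0.5 and median M of 28, 35 or 42 days. A share p of subjects sends every photo. There is no dropout, and assessments are accurate and on schedule.

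**Closed-form check.** Let F(t) = Φ[ln(t/M)/0.5]. On a photo day t, the proportion already *seen* closed is (1 − p)·F(v) + p·F(t), where v is the latest visit day up to t. The observed median is the first day on which this reaches 0.5. For M = 35, F(29) = 0.353, F(36) = 0.522, F(43) = 0.660 and F(57) = 0.835.

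- No photos: 0.353 seen closed at day 29, and nothing more until day 57 (0.835). The median is day 57, so the delay is 57 − 35 = 22 days.
- Half send photos: at day 43, 0.5 × 0.353 + 0.5 × 0.660 = 0.507, just past one half. In samples of 100 the median scatters mainly over days 43 and 50, averaging about 46. The delay is 46 − 35 = 11 days.
- All send photos: 0.522 at day 36. The median is mostly day 36, sometimes 43, averaging about 38. The delay is 38 − 35 = 3 days.

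**Simulation under these assumptions (n = 100), average medians in days:**

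| True median | Photos | Kaplan-Meier | Delay | Interval-censored |
|---|---|---|---|---|
| 28 | none | 36 | 8 | 28.5 |
| 28 | half | 30.5 | 2.5 | 28.0 |
| 28 | all | 30.7 | 2.7 | 28.2 |
| 35 | none | 57 | 22 | 37.5 |
| 35 | half | 46 | 11 | 35.2 |
| 35 | all | 38 | 3 | 35.3 |
| 42 | none | 57 | 15 | 44.0 |
| 42 | half | 56 | 14 | 42.3 |
| 42 | all | 45.5 | 3.5 | 42.5 |

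The interval-censored column is the Turnbull estimate with linear interpolation inside the interval that contains the median.

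**Other assumptions.**

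- Weibull healing (shape 2), 90% ever healing, normal visit windows, true medians of about 30 to 45 days: Kaplan-Meier is 11.9 to 20.4 days late with no photos, 5.5 to 13.3 with half and 3.0 to 4.3 with all. The interval-censored median is 0.4 to 1.9 days late.
- Visit windows, 15% of photos missed and 5% never healing: about 14 to 20, 5 to 13 and 4 to 5 days late. The interval-censored median stays within about 2.5 days.
- Weibull healing with the emergency visit windows and no photos: about 13 to 19 days late.

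Taken together, for true medians of about 28 to 43 days the delay is about 3 to 5 days (all), 2 to 14 (half) and 8 to 22 (none).

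**Area comparison.** With identical healing (M = 35), a group that all sends photos would report about 38 days and a group in which half do about 46. The 8-day gap would come from observation alone.

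**Precision of the alternative.** With no photos, fixed visit days and M of 35 or 42, the data place the Turnbull median only between days 29 and 57, an interval of 28 days. Interpolation supplies the rest. With photos in half the subjects the interval is about 7 days.

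**The case against.** The strongest reply is that the SAP says openly what it estimates. It dates closure at first observation, and for time to first *observed* confirmed closure the Kaplan-Meier estimate is sound. This stands. The delay exists only when the median is read as the time of closure, which the endpoint's name invites, so a clearer label is part of the answer.

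Second, photos are scheduled for every subject and are waived only when dressings may not be changed at home. A reader might infer that they are merely optional and take the no-photo figures as typical. The documents do not support that. Near full uptake the delay is only 3 to 5 days, and unscheduled visits would shorten it further. Uptake is not given, however, so a small delay cannot be assumed either.

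Third, a reader might infer that the 12-week gap after Week 12 distorts the median. It does not in any scenario run, because the medians fall before Week 12 or close to it. A closure first seen at the final Week 24 visit could not be confirmed two weeks later within the schedule, so it would be censored rather than dated late.

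Fourth, the size depends on where the true median falls relative to the visits. At 28 days, half and full photo uptake give almost the same answer (30.5 and 30.7).

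Finally, the Turnbull estimate has weaknesses of its own. It needs a convention inside the interval, and it assumes that assessment timing is unrelated to healing. Approval to remove dressings at home may itself depend on healing. Neither that nor misread photos (for example, drainage not visible) was modelled. These points argue for a supplement, not a replacement.

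**Conclusion.** The point holds in a limited form. As an estimate of when wounds close, the planned median is late, and the delay depends on photo uptake, which the documents do not give: about 3 to 5 days with photos from all subjects, 2 to 14 from half and 8 to 22 from none. These ranges assume true medians of about 28 to 43 days, the healing distributions shown, accurate assessments and no unscheduled visits.

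A reader might go further and infer that the area subgroups will appear to heal at different speeds. Nothing in the documents links photo use to treated area, so this is only a possibility if uptake differs. A reader might also infer that Kaplan-Meier is the wrong method and should go. The protocol specifies it, and it is valid for the date as defined. The endpoint is descriptive and not primary, and neither the adverse-event endpoint nor the Week 12 closure proportion uses this median. The change is still worth making because it relies on assessments already scheduled.

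**What to change.** In SAP 3.8.2:

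- Keep the protocol-specified Kaplan-Meier analysis, overall and by area, and label it *time to first observed confirmed closure*.
- Derive for each subject the last date any treated site was assessed as not closed and the first date all sites were seen closed (later confirmed), each with its source (visit or photo). State how a site that reopens before confirmation is handled.
- Add a supplementary Turnbull estimate of the curve and median, overall and for areas up to and above 500 cm². Report the interval that contains the median and the interpolation convention.
- Report photo uptake overall and by area.

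The cost is one extra derivation and one extra procedure, a wider and less familiar interval for the median, and reliance on assessment timing being unrelated to healing, which the report should state.
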